Random assignment will be followed by 8 weeks of treatment with NAC or placebo. Study medications will be identical in appearance. Participants will be provided with 10 days of medication at each weekly visit to increase the likelihood of medication continuity in case of a missed visit. Extra medication will be collected from participants at each visit. Study medication (NAC or placebo) will be started at a dose of 600 mg bid (1200 mg per day), for 3 days, then 1200 mg bid for 4 days, (2400 mg per day), then 1800 mg bid (3600 mg per day) for weeks 2 through 8. Similar doses have been shown to be an effective dose in other addiction studies (see A.2.). If the participant experiences significant side effects during the titration period, the dosage may be adjusted as necessary. Patients will be treated with the highest dose tolerated, not to exceed a total of 3600 mg per day, but may be reduced by 600mg increments as needed. Wellspring Compounding Pharmacy, a compounding Pharmacy – a compounding pharmacy recommended by the University of California, San Francisco School of Medicine Pharmacy -- will supply NAC study capsules and matching placebo capsules. The policies and procedures concerning good compounding practices and environmental, instrumental and procedural quality assurance have been approved by the California State Board of Pharmacy. The SFVAMC Research Pharmacist will directly receive all study medications from Wellspring Compounding Pharmacy and store in appropriate environmental conditions. The dosage is to be determined by a study physician at each weekly visit, using the titration schedule as a guide. An official VA prescription form must be filled out by a study physician for each patient at each visit. A research associate will pick up the prescription from the SFVAMC pharmacy. The date, time and amount of study compound dispensed will also be recorded in the subject's electronic medical file. Participants are instructed to return all unused study medication weekly. The number of returned capsules will be documented.

D.3.h. Medical Management

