Efforts will be made toward reducing the amount of missing data by: (a) use of a collateral informant to assist in locating patients; (b) telephone follow-up to make contact with missing patients; (c) establishment of flexible, but acceptable, time periods for the completion of each assessment; and (d) some self-report and interview measures may be administered by telephone to collect missing data from patients unwilling or unable to visit research sites to participate in a scheduled assessment session. All phone visits will include a Medical Management counseling session, during which a trained psychologist or psychiatrist (the Medical Manager) will assess adverse effects, concomitant medications, suicidality and general well-being. During phone visits, study coordinators will skip the question on the Adverse Event checklist, "Have you had suicidal thoughts or actions since the last study visit". Instead, the Medical Manager will ask that question and report back to coordinator after the Medical Management counseling session. If a Medical Management counseling session becomes logistically impossible, the PI will file a protocol violation.

Establishment of flexible, but acceptable time frames for completion of research assessments: All research assessments should be completed within an established window. Assessments scheduled for weeks 1, 2,3,5, 6, and 7 will have a window of ± 3 days for completion. Assessments scheduled for weeks 4, 8, and 12, have a window of ± 1 week for completion. This flexibility will enhance the ability of staff to schedule patients for assessments as close as possible to the protocol defined period. Patients likely to miss appointments should be scheduled early in the window to allow for successive attempts to complete ratings within the desired time frame.

After receiving CHR and R&D approval, we will be converting most of our questionnaire measures to a digital format, so that this questionnaire data can be collected and managed using the San Francisco VA Medical Center's Stress and Health Research Program Data Management Research Database System.

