Vital signs (temperature, heart rate, and blood pressure) will be measured weekly. Weight will be monitored monthly. The results will be recorded on a Vital Signs Form.

D.4.c.6. CONCOMITANT MEDICATIONS

All concomitant medications (prescription or over-the-counter medications) taken at the time of screening as well as those started during the study will be documented on a Concomitant Medication Form completed weekly.

D.4.c.7. CONCOMITANT TREATMENT

All concomitant treatments for mental health and well-being, with a focus on alcohol and substance use, PTSD and TBI will be recorded on a monthly basis. At screening, participants will be asked to report on the history of the mental health treatment. At weeks 4, 8, and 12 they will be asked to report on any new treatments they have started while in the study. Information will be recorded on the Concomitant Treatment form.

Veterans Alcohol TBI

D.4.c.8. ADVERSE EVENT (AE) MONITORING

All adverse events that occur between the first study-related procedure and the last study-related procedure will be reported. Serious adverse events occurring within 30 days following the last dose of study medication will also be handled according to this procedure. Those meeting the definition of serious adverse events will be reported using the Serious Adverse Event Form. Active monitoring of Adverse Events (AEs) will begin as soon as a study participant initiates study treatment, and will continue until the end of study for each participant. AEs will be monitored weekly in two ways:

- a. An open-ended question will be asked about presence of any AEs weekly (AE Spontaneous).
- b. A checklist of expected topiramate-related AEs will be asked of each participant weekly (AE Checklist).
- All Adverse Events will be recorded on the appropriate forms.

D.4.d. Alcohol and Substance Use Measures

D.4.d.1. TIMELINE FOLLOWBACK (TLFB)

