Review Medical Event Monitoring System (MEMS)	
Drug Accountability	
Dispense Medication	

D.5.c. Follow-up Phase

FOLLOW-UP PHASE The last visit, or follow-up, will take place on week 12. This visit will last between 3 and 3.5 hours.

FI. [name]
Measures
Concurrent Medications Form
Concurrent Treatments Form
AE Spontaneous Form
AE Checklist Form
TLFB – Timeline Followback
Demographics
CIWA – Clinical Institute Withdrawal Assessment for Alcohol, DSM-IV Version (CIWA-AD)
NSI – Neurobehavioral Symptom Inventory
AUDIT – Alcohol Use Disorders Identification Test
SIP-2R – Short Index of Problems
OCDS – Obsessive Compulsive Drinking Scales
PACS – Penn Alcohol Craving Scale
SHAS – Subjective High Assessment Scale
EVAR-B – Evaluation of Risks Scale
PCL – PTSD Checklist
POMS – Profile of Mood States
BDI-II – Beck Depression Inventory
BAI – Beck Anxiety Inventory
BIS-11 – Barrett Impulsivity Scale
PSQI – Pittsburgh Sleep Quality Index
ISI – Insomnia Severity Index
DERS – Difficulties in Emotion Regulation Scale
DTS – Distress Tolerance Scale
APT – Alcohol Purchase Task
WTAR - Wechsler Test of Adult Reading
HVLT-R – Hopkins Verbal Learning Test
TMT A + B – Trail Making Test A & B
WAIS 4 – Arithmetic
WAIS 4 – Antimetic WAIS 4 – Digit Span
Stroop Inhibition
COWA – Controlled Oral Word Association
BART – Balloon Analogue Risk Task
IGT – Iowa Gambling Task
SST – Stop Signal Task
AAT – Alcohol Approach Task
End of Study Completion Questionnaire
Procedures
Breath Alcohol Concentration (BrAC)
Clinical Labs – renal panel, hepatic panel and GGT
Ethyl Glucuronide (EtG)
Urine Drug Screen
Phosphatidylethanol (PEth)
Vitals (Blood pressure, heart rate, temperature)
Weight
Assess birth control method and perform urine pregnancy test (women only)
Drug Accountability
Dispense Medication

D.6. DATA ANALYSIS

The proposed study has primary, secondary, and exploratory outcomes.

D.6.a. Primary Outcome Measure

PI: [name] The primary outcome measure will be the change in number of drinking days from baseline to end of study, associated with NAC treatment.

1) Primary Hypothesis

The *Primary* hypotheses are that NAC treatment will be more efficacious than placebo in reducing PHDDs and TBI symptom severity (NSI).

2) Data Analytic Technique for the Primary Outcome

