Adverse Events (AEs) will be collected using the definition of the UCSF IRB and International Conference on Harmonization (ICH) for Clinical Safety Data Management (ICH-E2A), according to which an adverse event is "any untoward medical occurrence in a patient or clinical investigation participant administered a pharmacological product which does not necessarily have to have a causal relationship with this treatment." An AE can therefore be any unfavorable or unintended sign (including an abnormal laboratory finding), symptom, or disease temporarily associated with the study intervention. This includes any occurrence that is new in onset or aggravated in severity or frequency from the baseline condition, or abnormal results of

diagnostic procedures including laboratory test abnormalities.

E.1.c.3. Serious adverse event definition

Research staff will immediately notify the study physician in the event of a serious adverse event (SAE). In the event of one that is life-threatening or requires hospitalization, the participant's medical status will be monitored and the decision of whether to withdraw the participant from the study will be made on an individual basis by the study physician based on severity and nature of the medical problem. For all adverse reactions that are serious, life-threatening, or require hospitalization, the principal investigator and research coordinator will notify the UCSF IRB and the Federal Drug Administration (FDA) using the standard procedures provided by each agency. An FDA adverse reaction form will be completed at that time.

E.1.d. Participant Withdrawal

Participants will be withdrawn from the study if:

- in the clinical judgment of the investigator, the participant requires acute detoxification from alcohol,
- in the clinical judgment of the investigator, the participant's clinical condition worsens substantially (for example, if weekly alcohol use increases 25% or more over baseline) and it is felt to be in the participant's best interest to obtain alternative treatment including, but not limited to, additional psychotherapy, pharmacotherapy, hospitalization, etc.
- the participant becomes pregnant. Should a participant become pregnant at any time during the study the participant will immediately discontinue study medication. Study medication will not be tapered.

E.2. DATA AND SAFETY MONITORING

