E.2.a. Plan to Monitor Study Progress and Safety: The Data and Safety Monitoring Plan_(DSMP) The DSMP for this project consists of:

- a Data and Safety Monitoring Board (DSMB)
- a schedule of DSMB meetings to review study data and events
- a list of study data and event items to be reviewed by the DSMB
- procedures for communicating DSMB findings to the UCSF IRB, and other appropriate entities
- a plan for conducting and reporting interim analysis
- stopping rules
- rules for withdrawing study participants from the study interventions

Note: These elements of the DSMP are described below:

E.2.b. The Data and Safety Monitoring Board (DSMB)

The Data and Safety Monitoring Board (DSMB) is a group of 3 physicians who are clinicians as well as clinical researchers, and who are not study investigators. They have expertise in the areas of clinical psychiatry, clinical psychopharmacology, neurocognitive functioning, traumatic brain injury and substance use disorders. The composition of the DSMB is: [name]., M.P.H., Staff Psychiatrist, SFVAMC; [name]., Staff Psychiatrist, SFVAMC; and [name]., SFVAMC.

The DSMB will meet quarterly to review data reports prepared by the PI regarding the progress of the study and will monitor patient enrollment, retention, outcomes, adverse events, and other issues related to patient safety. The DSMB will make recommendations to the PI as to whether the study should continue or be modified or terminated. The DSMB can consider patient safety or other circumstances as grounds for early termination. Any member of the DSMB can ask for a meeting of the group if he/she feels that it is necessary, based upon the data.

During the course of the study, reports will be prepared and distributed to the Data and Safety Monitoring Board on a quarterly basis. In order for the Data and Safety Monitoring Board to discharge their duties for overseeing the study and the rights of the patients, they will receive analyses of the primary outcome measures and the important exploratory measures on a quarterly basis. The DSMB will receive reports of serious adverse events (SAEs) within 72 hours of their occurrence. DSMB Minutes will be prepared by the Study Coordinator within 5 working days after each quarterly DSMB meeting.

E.2.c. Research Monitor

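### The 30-day post-dose SAE window is not assured by any scheduled contact: nominal week 12 falls 28 days after the last dose, and no safety contact is specified after withdrawal

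*Combined protocol and SAP*

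**What the plan says.** Section D.4.c.8 (Adverse Event Monitoring) contains three rules. Adverse events are reported from the first to the last study-related procedure. For serious events, "Serious adverse events occurring within 30 days following the last dose of study medication will also be handled according to this procedure". Active monitoring starts with study treatment and "will continue until the end of study for each participant".

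The schedule around that rule is as follows.

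- D.3.g: "Random assignment will be followed by 8 weeks of treatment with NAC or placebo". Also, "Participants will be provided with 10 days of medication at each weekly visit", with unused drug collected at each visit.
- D.4.a: "Assessments scheduled for weeks 4, 8, and 12, have a window of ± 1 week for completion". Participants who are missing are to be followed up by telephone, and phone visits include an assessment of adverse effects.
- D.5.c: "The last visit, or follow-up, will take place on week 12".
- D.4.b.6: a form completed at week 12 or at termination records the last day on which study medication was taken.
- E.1.d: "Participants will be withdrawn from the study if" one of several conditions is met, among them need for detoxification, substantial worsening, or pregnancy. E.2.h adds unacceptable adverse events related to the interventions.

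Section D.5 lists no contact after week 12, and no section specifies a safety contact after termination.

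**The concern.** The SAE rule is counted from the last dose, while active monitoring is counted to the participant's end of study. The two end points need not coincide. For someone who completes treatment, the last visit can come before day 30 after the last dose. For someone withdrawn from the study, active monitoring may end at about the time the 30 days begin.

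The second gap matters more. It falls on people removed because they worsened or had unacceptable adverse events, and a serious event shortly after stopping is of most interest in that group. Safety and tolerability are stated purposes of the pilot (D.1.a), and multiple related SAEs are an example of a stopping concern (E.2.g). With 30 participants, a single missed SAE would change the safety summary.

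**Working it through.** The 30 days is a rule, not a derived figure, so there is nothing to reproduce. The check is date arithmetic, taking week k as day 7k.

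**Inputs.** SAE window 30 days (D.4.c.8); treatment 8 weeks and supply 10 days per visit (D.3.g); last visit week 12 (D.5.c); window ±7 days at weeks 8 and 12 (D.4.a).

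**Step 1: nominal case.**
- Last dose: 8 × 7 = day 56. Window closes: 56 + 30 = day 86.
- Week 12: 12 × 7 = day 84. Gap: 84 − 56 = 28 days, which is 2 days short.

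**Step 2: week-12 window, last dose on day 56.**
- Permitted days: 84 − 7 = 77 to 84 + 7 = 91.
- Gap: 77 − 56 = 21 days to 91 − 56 = 35 days.
- A visit on days 86 to 91 reaches 30 days; one on days 77 to 85 does not.

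**Step 3: who is covered if they keep attending.** Latest last-dose day covered = visit day − 30.
- Nominal visit: 84 − 30 = day 54.
- Earliest visit: 77 − 30 = day 47.
- Latest visit: 91 − 30 = day 61.
- Example: a participant who stops drug on day 28 and attends nominal week 12 is seen 84 − 28 = 56 days later, so is covered.

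**Step 4: how far the last-dose date can move.**

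| Assumed last dose | Gap at nominal week 12 | Gap over the week-12 window |
|---|---|---|
| Day 56 | 28 days | 21 to 35 days |
| Tied to the week-8 visit (day 49 to 63) | 35 to 21 days | 14 to 42 days |
| 10-day supply from week 7 used up (49 + 10 = day 59) | 25 days | 18 to 32 days |
| 10-day supply from week 8 used up (56 + 10 = day 66) | 18 days | 11 to 25 days |

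The last two rows are upper cases. The week-7 row needs the spare doses to be taken before the week-8 visit collects them. The week-8 row applies only if drug is dispensed at week 8. D.5.b lists dispensing at week 8 and lists weeks 9, 10 and 11 as treatment visits, and D.5.c lists dispensing at week 12. These entries conflict with the 8-week treatment period in D.3.g, so the nominal last dose of day 56 is itself provisional.

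**Step 5: withdrawal, by comparing sections.** E.1.d and E.2.h both say that participants are withdrawn from the study. D.4.b.6 separates termination from completion at week 12. D.4.c.8 ends active monitoring at the participant's end of study. Read together, no contact is specified in the 30 days after a withdrawn participant's last dose. The telephone provisions in D.4.a serve missing patients and missed scheduled assessments, and they are not linked to the 30-day window.

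**The case against.** The strongest reply is that the quoted sentence is a handling rule. It says how an SAE in the 30 days is processed and does not promise active capture. An SAE reported spontaneously after week 12, or after withdrawal, still falls under it. This stands: the window is covered by the rule, but its ascertainment is not assured by a scheduled contact.

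A reader might infer that participants who stop early have no later contact at all. The documents do not say so. D.4.a plans collateral informants and telephone follow-up. E.1.a.4 lets staff verify the safety of those who miss several appointments. D.2.a obtains permission to consult treating clinicians. Intent-to-treat analysis of all randomized participants is planned. E.2.h is also headed as withdrawal from the interventions, although its text says from the study. None of this sets a contact at 30 days, but it rules out the stronger claim.

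A reader might also put a percentage on the problem. Two candidates fail.
- Six of the 15 permitted week-12 days reach day 86. That counts calendar days, not participants, and nothing shows that visits spread evenly over the window.
- The team's topiramate trial reported 81.25% attendance at its final visit, which would give 30 × (1 − 0.8125) = 5.6 participants not attending. That trial was small and unfinished and used a drug that the protocol describes as having a much higher adverse event profile. Missing week 12 also does not show that a participant had no contact within 30 days of the last dose.

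Finally, the nominal shortfall for completers is only 2 days, and a late week-12 visit within the window closes it. That is correct, and this limb alone would be minor.

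**Conclusion.** The point holds in a limited form. The plan sets a 30-day post-dose SAE window, but no scheduled contact assures that events in it are found. For completers the nominal gap is 28 days, with a range of 21 to 35 days, on the assumption that the last dose is on day 56. For participants withdrawn from the study, no safety contact is specified, and this is the more important part.

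Participants whose last dose is by day 54 and who attend nominal week 12 are covered. How many others would be missed cannot be derived from the documents, and no post-dose SAE rate is given. A reader might infer a safety estimate biased between arms; uneven withdrawal could produce that, but nothing in the documents shows it.

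The change is worth making because it is cheap and improves safety capture where it is weakest.

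**What to change.** - In D.4.c.8 and D.5.c, require one SAE check at or after 30 days from the actual last dose for every participant who took any study drug. Do it at the week-12 visit if that visit falls late enough, otherwise by telephone. The form in D.4.b.6 already records the last-dose date, and D.4.a already provides for telephone assessment.
- In E.1.d and E.2.h, state that withdrawal does not end this safety contact.
- Reconcile the week 9 to 11 treatment visits in D.5.b, and the dispensing entries at week 8 (D.5.b) and week 12 (D.5.c), with the 8-week treatment period in D.3.g, so that the last-dose date is defined.

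The cost is protocol wording and one short call for some participants, with no new visit or test. Some participants who have left may not answer, so the form should record whether SAE status at 30 days was ascertained.

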Prospective participants will undergo a brief CPRS pre-screen (**see CPRS Screen**) and an in-person or telephone pre-screen (**see Phone Screen**) to establish that they are: 18-69 years of age, screen positive for TBI, drink at hazardous or harmful levels by NIAAA criteria⁸ and wish to reduce or stop alcohol use.

D.3.d. Consent

Breath Alcohol Test Prior to Consent

If the breath alcohol test reading is greater than 0.00%, the participant will be asked to return later that day, or on another day, to be retested.

Consenting

After passing the pre-screen, participants will provide written informed consent in compliance with IRB

PI: [name] regulations. During the consent process, Veterans are asked to abstain from driving to study visits while intoxicated. They are informed that if they do drive and their breath alcohol level is above 0.08, then a clinician will assess their safety before they are allowed to leave the SF VA Medical Center.

D.3.e. Screening

After consent, participants will be scheduled for screening assessments. The screening phase is accomplished over a total of approximately three to four visits extending over one week.

D.3.f. Random Assignment

Participants will be randomly assigned, sequentially as they qualify for the study, to either NAC or placebo in a 1:1 ratio per a computer-generated list provided by a biostatistician. Randomization will be balanced using permuted blocks. Participants and investigators will be blinded to assignment. To maintain the blind, sealed envelopes containing the study drug identification (e.g. NAC or placebo) will be kept together, in a limited access area (the study pharmacist's office) that will be available to the investigators should the blind need to be broken for any individual participant.

D.3.g. Pharmacotherapy

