Participants will be compensated in cash or check for their time, effort and travel costs after each completed visit. The screening visits at baseline will be reimbursed based on the completion of tasks up to \$85. The payment schedule for baseline/screening measures and procedures is listed below. Participants will receive \$20 for completed visits on Weeks 1, 2, 3, 5, 6, and 7. The longer visits of Weeks 4 and 8 will be compensated at a rate of \$35 and the follow-up visit \$40. Participants will also be paid \$5 at each study visit during weeks 1-8 for returning study medication bottles. Additionally, if participants attend all 9 study visits, they will receive an additional \$50 at the follow-up visit. Details regarding compensation are outlined below and in the informed consent form. Participants can therefore earn up to a total of \$410 for the full 12-week study participation.

If a participant lives outside of the San Francisco city limits and it takes over an hour to get to the SFVAMC, then the participant will receive \$0.51 per mile (NCIRE travel reimbursement policy). Mileage will be calculated using the Google maps "DIRECTIONS" function, using the participant's home address as the starting point and the SFVAMC address as the point of destination.

PAYMENT SCHEDULE FOR BASELINE/SCREENING MEASURES/PROCEDURES

MEASURES/PROCEDURES	AMOUNT
Informed Consent	
TLFB/Patient Locator	\$10
SCID	\$5
TBI Evaluation	\$10
CTSI	\$10
Self-report measures – (21 total)	\$20
Neurocog	\$20
Med Mgmt	\$5
AEs/ConcomMeds/Concom Txt	\$5
TOTAL AMOUNT	\$85

WEEKLY COMPENSATION SCHEDULE

Week Attend study visit		Return MEMS cap	Attend all study visits	Total per visit
Screening Visits	\$85*			\$85
Week 1	\$20	\$5		\$25
Week 2	\$20	\$5		\$25
Week 3	\$20	\$5		\$25
Week 4	\$35	\$5		\$40

	\$405			
Week 12	\$40		\$50	\$90
Week 8	\$35	\$5		\$40
Week 7	\$20	\$5		\$25
Week 6	\$20	\$5		\$25
Week 5	\$20	\$5		\$25

D.4. MEASURES AND SCHEDULE OF DATA COLLECTION

D.4.a Overview (See Table 1 for Schedule of Measures)

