There are future plans to bring in an additional server machine configured as an application server as well as a library tape system.

Study management is further supported by a Clinical Trial Management System (CTMS) application providing the ability to track many aspects of a clinical trial. Study start-up includes numerous administrative and clinical activities. All of these tasks involve tedious, manual process for collecting and aggregating information from different data sources. The CTMS system consolidates these efforts (i.e. reduce duplications and inconsistencies) and provide efficiencies and cost savings for the clinical operations. Users also manage recruitment outreach activities, track recruitment progress, and search through a pool of potential participants for future studies. The system provides real-time and comprehensive study management metrics to support the day-to-day business operations. This CTMS system is a commercial off-the shelf product that hooks into the research database server for added data integration.

D.4.b. General Measures

D.4.b.1. PATIENT SCREENING LOG

Written informed consent will be obtained prior to screening for study eligibility and completion of baseline assessments. All patients who undergo eligibility screening will be listed on the Patient Screening Log to provide information about the number of patients screened.

D.4.b.2. PATIENT LOCATOR INFORMATION

This form includes information about how to contact the participant.

D.4.b.3 BASELINE ASSESSMENTS

Measures will be recorded on several forms and will include demographic information (such as age, gender, race, and ethnicity), work history, medical history, physical examination, laboratory evaluation DSM-IV psychiatric diagnoses, alcohol, substance use, and cigarette smoking history, current medications, and family history.

D.4.b.4 ELIGIBILITY FORM

The listing of inclusion and exclusion criteria will serve as a screening format for eligibility which will be completed following baseline assessments.

D.4.b.5. MAINTENANCE OF THE BLIND

This questionnaire is administered at Week 12 to assess the maintenance of participants' and physicians' blindness. Participants are asked to speculate on their assignment to either topiramate or placebo. Each participant's treating physician is also asked to speculate on the participant's assignment to topiramate or placebo.

D.4.b.6. STUDY COMPLETION/TERMINATION FORM

Veterans Alcohol TBI

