The study will be stopped if, in the judgment of the DSMB or the PI, there are sufficient safety concerns that arise during the conduct of the study that would indicate that participants are being harmed by study interventions. Examples of such safety concerns would be:

- If, after the first 10 participants (33% of the planned enrollment) have completed their study treatment, the interim analysis reveals that more than 50% (i.e. 6 participants) have worsened to a clinically significant degree in the primary outcome measure of alcohol use from baseline to study end.
- Other events that pose unacceptable risks to participants, e.g., multiple SAEs that are judged to be related to study interventions

E.2.h. Rules for Withdrawing Study Participants from the Study Interventions

Participants will be withdrawn from the study if, in the opinion of the DSMB or the PI, there is: sustained clinically significant worsening in the primary outcome measure of alcohol use, unacceptable adverse events judged to be related to study interventions, or any other clinically significant medical, psychiatric, or substance use related poor outcome that makes continued study participation unsafe in the clinical judgment of the PI or DSMB members.

E.2.i. Rules for Breaking the Blind

The blind will be broken for an individual in the study if, in the opinion of the PI or DSMB, there is an emergent clinical need to determine whether a participant is receiving NAC or placebo.

E.3. BENEFITS TO TAKING PART IN THE STUDY

Participants may benefit from the extra physical examination, laboratory tests, and attention to and treatment

PI: [name] of alcohol use disorders. In the informed consent form, participants are instructed: "Taking part in this study may or may not make your health better. If you are in this study, you may benefit from the physical examinations, blood tests, and review of your symptoms. You may respond favorably to the treatment and reduce your drinking and brain injury symptoms, but there is no guarantee that this will happen. Others may benefit from the overall conclusions drawn from the results of this study."

E.4. IMPORTANCE OF THE KNOWLEDGE TO BE GAINED

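### The weekly adverse-event checklist and the Week 12 blinding questionnaire are specified for topiramate, which is not a treatment in this trial; the checklist is the part that matters

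*Combined protocol and SAP*

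**What the plan says.** The arms are not in doubt. Section D.3.f assigns participants "to either NAC or placebo in a 1:1 ratio per a computer-generated list provided by a biostatistician", and the unblinding rule in E.2.i applies when "there is an emergent clinical need to determine whether a participant is receiving NAC or placebo".

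Two data-collection instructions name a different drug:

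- D.4.c.8 (Adverse Event Monitoring) gives two weekly methods. The first is general: "An open-ended question will be asked about presence of any AEs weekly (AE Spontaneous". The second is drug-specific: "A checklist of expected topiramate-related AEs will be asked of each participant weekly (AE Checklist".
- D.4.b.5 (Maintenance of the Blind) sets a Week 12 questionnaire. "Participants are asked to speculate on their assignment to either topiramate or placebo", and each participant's "treating physician is also asked to speculate on the participant's assignment to topiramate or placebo".

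No later text corrects either instruction. The protocol has its own NAC effects, listed by body system in E.1.a.2 and as participant information in E.1.b.2, but D.4.c.8 does not link the checklist to them. The Week 12 list in D.5.c includes the AE Checklist Form and an "End of Study Completion Questionnaire". It does not name the blinding questionnaire.

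**The concern.** Topiramate appears properly in the background sections as the group's previous research. The two instructions above are different, because they define the content of forms used in this trial.

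The checklist is the only itemised adverse-event prompt in the weekly schedule. The protocol describes topiramate's problems mainly as cognitive (B.5, C.5). Its NAC lists are mostly dermatologic, gastrointestinal, cardiovascular and allergic. A checklist built for one drug cannot be assumed to ask about the effects of the other.

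The safety data have a stated use. Safety and tolerability are part of the reason for the pilot (D.1.a), estimates of harm are planned (the subsection of D.3.i on estimates for a larger study), and the DSMB reviews adverse events (E.2.b, E.2.e). For blinding, the concern is simpler: someone on NAC who answers the question literally has no correct choice.

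**Working it through.** The plan states no figure on this point, so the check is a comparison of sections plus one short piece of algebra.

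**1. Arms against forms.** D.3.f and E.2.i: NAC or placebo. D.4.c.8 checklist: topiramate effects. D.4.b.5 questionnaire: topiramate or placebo, for both kinds of respondent. The forms therefore disagree with the randomisation.

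**2. What else can capture a NAC effect.** The weekly open-ended question (D.4.c.8), weekly vital signs (D.4.c.5), weekly CIWA-AD and the other safety evaluations (D.4.c.1), discussion of medication effects in Medical Management (D.3.h), adverse-effect assessment at phone visits (D.4.a), and repeat renal and hepatic panels (D.4.c.3). Participants also receive a list of adverse effects at consent (E.1.b.2). What is not assured is prompted elicitation of the listed NAC effects.

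**3. What is known of the form.** It is not reproduced. D.4.a quotes one item, on suicidal thoughts or actions, which refers to no drug. The working form may therefore be broader than its one-line description, but its overlap with the NAC lists is unknown.

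**4. Effect of lower sensitivity on the arm comparison.** Let p1 and p0 be the true risks of a given event on NAC and placebo, and let s (between 0 and 1) be the probability that a true event is recorded. Assume s is the same in both arms and that no false events are recorded.

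- Observed risks: s × p1 and s × p0
- Observed difference: s × p1 − s × p0 = s × (p1 − p0)
- Observed ratio: (s × p1) / (s × p0) = p1 / p0

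Whenever s is below 1, the absolute difference moves toward zero. The ratio is preserved in expectation but rests on fewer events. No value of s can be derived from the documents.

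**5. Blinding guess.** Planned enrolment is 30 at 1:1, and 30 / 2 = 15, so about 15 participants on NAC, and the physician guesses for the same 15, have no literally correct option. Neither D.6 nor the statistical text in D.3.i plans an analysis of these guesses.

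**6. The same carry-over elsewhere.**

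- D.4.e.1 names topiramate twice in an instruction for analysing the NSI, one of the two outcomes in the primary hypotheses.
- Ten purpose lines name it once each: BDI, BAI, Iowa Gambling Task, Digit Span, Arithmetic, COWA, HVLT, Trail Making, WTAR and Stop-Signal.
- The power text in D.6.a refers to a topiramate arm of the proposed trial. The pilot effect size of d = 1.87 in the same paragraph is a genuine topiramate result and is not an error of this kind.

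**The case against.** The best defence is that these are leftovers from a template and that little depends on them. Much of that is fair. The open-ended question is not tied to any drug, several other routes can record events, and one known checklist item is generic. The consent wording quoted in E.1.b.2.a names NAC, so respondents may well read topiramate as meaning the active drug, and a one-line recode would make the guesses scorable. What remains is that no recode is stated and nothing in the plan assures that NAC effects are prompted for.

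Several stronger readings are tempting, and the documents do not support them:

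- *NAC adverse events will be missed.* The routes in step 2 remain open. Only prompting is in question.
- *The same checklist in both arms makes the comparison neutral, or else it favours one arm.* Neither follows. Under equal sensitivity the absolute difference shrinks toward zero, by an unknown amount.
- *The scale can be shown by counting checklist administrations.* Such a count measures no lost events. The schedule is also inconsistent: D.3.k refers to 9 study visits, while D.5.b lists weeks 9, 10 and 11 as well.
- *The blinding questionnaire will not be collected.* D.4.b.5 orders it at Week 12. The D.5 lists are not exhaustive (Delay Discounting, set for baseline and weeks 4, 8 and 12 in D.4.h.1.b, is in none of them), and the Table 1 schedule cited in D.4.a is not in the supplied text. All that is shown is that D.5.c does not name it.
- *The forms in use carried the topiramate wording.* The documents do not say.

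**Conclusion.** The inconsistency is real and should be corrected. The checklist carries the weight: as specified, it does not assure prompted elicitation of NAC effects in a pilot meant to inform on safety and tolerability. The consequence is possible under-recording, which would pull an absolute NAC-placebo difference toward zero. That direction rests on equal sensitivity in the two blinded arms and no false reports, and the size cannot be stated without the form.

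The blinding part is minor. About 15 NAC participants and their physicians have no literally correct option, but no planned result uses the answers. No efficacy result depends on either instrument.

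**What to change.** Reconcile D.4.c.8 and D.4.b.5 with D.3.f and E.2.i:

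- Base the AE Checklist on the protocol's own NAC effects (E.1.a.2, E.1.b.2), noting that by the protocol's account most of the effects listed in E.1.a.2 come from intravenous use. Keep the open-ended question and the suicidality item that D.4.a relies on.
- Change the blinding options to NAC or placebo for participants and physicians. Name the questionnaire in the D.5.c list and check that Table 1 agrees.
- Confirm and document which form versions were used. If the topiramate wording was fielded, write the handling rule before unblinding: for example, score a topiramate guess as active treatment, and state which NAC effects the fielded checklist did prompt for.
- Correct the NSI analysis instruction in D.4.e.1 to the NAC arm, the ten purpose lines in D.4.g and D.4.h, and the reference to a topiramate arm of this trial in D.6.a. Leave the prior pilot effect size there as it is; the basis of the power calculation is a separate issue.

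The cost is two form specifications, one schedule line, wording edits, a version check and, if needed, a short handling rule. No visits, staff or procedures are added.
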